7.1 Definitions

7.1.1 Adverse Event

An **adverse event** (AE) is any symptom, sign, illness or experience that develops or worsens in severity during the course of the study. Intercurrent illnesses or injuries should be regarded as adverse events. Abnormal results of diagnostic procedures are considered to be adverse events if the abnormality:

- results in study withdrawal
- is associated with a serious adverse event
- is associated with clinical signs or symptoms
- leads to additional treatment or to further diagnostic tests
- is considered by the investigator to be of clinical significance

For FDA regulated studies the FDA defines an adverse event as the following: any untoward medical occurrence associated with the use of a drug in humans whether or not considered drug related.

7.1.2 Serious Adverse Event

Adverse events are classified as serious or non-serious. A **serious adverse event** is any AE that is:

- fatal
- life-threatening
- requires or prolongs hospital stay
- results in persistent or significant disability or incapacity
- a congenital anomaly or birth defect
- an important medical event

Important medical events are those that may not be immediately life threatening, but are clearly of major clinical significance. They may jeopardize the subject, and may require intervention to prevent one of the other serious outcomes noted above. For example, drug overdose or abuse, a seizure that did not result in in-patient hospitalization or intensive treatment of bronchospasm in an emergency department would typically be considered serious.

All adverse events that do not meet any of the criteria for serious should be regarded as **non-serious adverse events**.

7.2 Recording of Adverse Events

At each contact with the subject, the investigator will seek information on adverse events by specific questioning and, as appropriate, by examination. Information on all adverse events will be recorded immediately in the source document, and also in the appropriate adverse event module of the case report form (CRF). All clearly related signs, symptoms, and abnormal diagnostic procedures results should be recorded in the source document, though should be grouped under one diagnosis.

All adverse events occurring during the study period will be recorded. The clinical course of each event will be followed until resolution, stabilization, or until it has been determined that the study intervention or participation is not the cause. Serious adverse events that are still ongoing at the end of the study period will be followed up to determine the final outcome. Any serious adverse event that occurs after the study period and is considered to be possibly related to the study intervention or study participation will be recorded and reported immediately.

7.3 Relationship of AE to Study

The relationship of each adverse event to the study procedures should be characterized. The PI or medical monitor will determine how the relationship of the AE will be classified as:

- likely related – a well-known effect of the device or clearly not related to the subject or environmental factors
- probably related – is known or suspected effect of device or cannot be readily explained by subject or study procedures
- possibly related – is a possible effect of the device or can be explained by the subject or study procedures
- unlikely related – is not a suspected effect of the device or can readily be explained by the subject or environmental factors
- unrelated – is not a known effect of the device and can readily be readily and easily explained by the subject or environmental factors

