7.4.2 Investigator reporting: notifying the study sponsor

Investigators from all participating sites should report all unexpected and related adverse events, regardless of whether they are serious or not, and all unanticipated problems to the sponsor.

Any study-related unanticipated problem posing risk to subjects or others, and any type of serious adverse event, will be reported to the study sponsor by telephone within 24 hours of the event. To report such events, a Serious Adverse Event (SAE) form will be completed by the investigator and emailed to the study sponsor within 24 hours. The investigator will keep a copy of this SAE form on file at the study site. Report serious adverse events by sending via email to: [Evolus., Company Call Center: [name] ([name]), Company Email: [contact]]

Within the following 48 hours, the investigator will provide further information on the serious adverse event or the unanticipated problem in the form of a written narrative. This should include a copy of the completed Serious Adverse Event form, and any other diagnostic information that will assist the understanding of the event. Significant new information on ongoing serious adverse events should be provided promptly to the study sponsor.

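### The causality scale in section 7.3 lets one adverse event meet up to four of five grades and has no test for a procedure effect, leaving three narrow safety rules on an ambiguous footing

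*Combined protocol and SAP*

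**What the plan says.** The opening of section 7.3 states the aim: "The relationship of each adverse event to the study procedures should be characterized". The choice among five grades falls to the investigator or medical monitor. In substance they are:

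- *Likely*: an established device effect, or plainly no cause in the subject or environment.
- *Probably*: a device effect that is at least suspected, or an event that neither the subject nor a study procedure readily accounts for.
- *Possibly*, in the section's words: "is a possible effect of the device or can be explained by the subject or study procedures"
- *Unlikely*: no device effect suspected, or else a ready explanation in the subject or environment.
- *Unrelated*: no known device effect, together with a ready and easy explanation of that kind.

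The section gives no order of precedence and no rule for an event that meets more than one grade.

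Three rules elsewhere turn on relatedness or cause. Under section 7.4.2, investigators "should report all unexpected and related adverse events, regardless of whether they are serious or not". Under section 7.2, a serious event after the study period is recorded and reported if "considered to be possibly related to the study intervention or study participation". Section 7.2 also lets follow-up of an event end once the intervention or participation is judged not to be its cause.

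**The concern.** Two separate flaws sit in the same five lines.

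The first is the place given to study procedures. The section says it will grade relationship to them, but no grade has a positive test for a procedure effect. Where procedures do appear, in *probably* and *possibly*, they stand beside the subject as an alternative to the device. What is being assessed is thus used as a competing explanation.

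The second is the connective. *Likely*, *probably*, *possibly* and *unlikely* are each satisfied by either of two tests; only *unrelated* needs both. The grades therefore overlap, and two careful assessors could apply the text correctly and give the same event different grades.

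At stake is whether certain events reach the sponsor, and when follow-up of an event may stop. Section 9.1 names rare but grave consequences of injection into a vessel, so the causality wording deserves to be unambiguous.

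**Working it through.** The plan gives no figure here, so the check is a reading of the logic. The inputs are the five definitions in 7.3. Device-effect levels are taken as nested: well-known implies known, known implies suspected, suspected implies possible.

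**Upper limit.** *Likely* needs a well-known device effect, or a clear absence of any subject or environmental cause. *Unrelated* needs an effect that is not known, together with a ready explanation from the subject or environment. Each limb of *likely* contradicts a condition of *unrelated*, so no event can meet all five. The maximum is four.

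**Is four reached?** Yes, in two patterns, and a third case shows the procedure problem:

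| Event | Likely | Probably | Possibly | Unlikely | Unrelated |
|---|---|---|---|---|---|
| Well-known device effect, also readily explained by the subject | yes | yes | yes | yes | no |
| Suspected but not known device effect, also readily and easily explained by the subject | no | yes | yes | yes | yes |
| No suspected or possible device effect, readily explained by the injection procedure alone | only if subject and environment are clearly ruled out | no | yes | yes | no |

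In the third row, *possibly* is met because a study procedure explains the event. *Unlikely* is met because the event is not a suspected effect of the device. An event caused wholly by a study procedure can thus be graded *unlikely*, against the aim stated at the head of the section.

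**How general is the overlap?** The definitions were coded literally and run over five levels of device effect, five of subject explanation, five of environmental explanation and three of procedure explanation: 5 × 5 × 5 × 3 = 375 combinations.

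- As written: 101 combinations met two grades, 186 met three and 88 met four (101 + 186 + 88 = 375). None met exactly one.
- With study procedures removed as a rival explanation but 'or' kept: the maximum is still four. The overlap therefore comes from 'or', and the procedure wording is a distinct fault.
- With 'or' simply replaced by 'and': the maximum falls to three, but 33 of 375 combinations meet no grade.

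The counts depend on how the levels were coded. The maximum of four follows from the wording.

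**What the grade affects:**

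| Rule | Depends on relatedness or cause? |
|---|---|
| Recording of all study-period events (7.2) | No |
| Any serious event to the sponsor within 24 hours (7.4.2) | No |
| Unexpected non-serious events to the sponsor (7.4.2) | Yes |
| Serious events after the study period (7.2) | Yes |
| End of follow-up (7.2) | Yes |

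**The case against.** The strongest reply is that this is an ordinal scale applied by clinical judgement in a single-centre descriptive series of about 10 subjects, and that other rules catch most of what matters. Much of that stands. Study-period events are all recorded, and any serious event goes to the sponsor whatever its grade, as do study-related unanticipated problems posing risk. Section 7.4 adds that other events and complaints are handled under institutional and federal policies. The post-study rule in 7.2 already names participation as a possible cause. What remains exposed is limited to the three rules above.

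Four stronger readings are tempting but unsupported:

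- *That the scale biases grades downward.* The 'or' also permits upgrading: anything clearly not due to the subject or environment is *likely*. The text shows ambiguity, not direction.
- *That naming study procedures as a rival pushes events below the line.* The phrase occurs only in *probably* and *possibly*. The route to *unlikely* is the device-only test in that grade.
- *That common effects such as bruising would go unreported.* Bruising is a listed risk in 9.1, hence expected, so the rule for unexpected events would not capture it at any grade. Ordinary bruising is not serious either. It can illustrate overlap, not a lost report.
- *That a related-event rate would be distorted.* The plan specifies no such rate, so there is no planned estimate to be wrong.

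One might also read 'device' as including its injection. The *probably* and *possibly* definitions name device and study procedures separately, and the schedule of study procedures has an intervention column, so the text does not support merging them.

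**Conclusion.** The point holds as a defect in a stated rule, not as missing detail. The definitions contradict the section's own aim and allow up to four of five grades for one event, including *unlikely* for an event caused only by the injection procedure. The second four-grade pattern matters most in practice: a suspected but not established effect can be graded anywhere from *probably* to *unrelated*, and if it is unexpected and non-serious the choice may decide whether the sponsor hears of it.

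The consequence is confined to that sponsor rule, serious events after the study period and the end of follow-up. The primary endpoint is unaffected.

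The conclusion rests on a literal reading of the definitions and on nested effect levels. The link to reporting further assumes that *unlikely* and *unrelated* count as not related. The documents do not say which grades count, which is itself a reason to revise the section.

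**What to change.** Reword 7.3 so that device or study procedure ('either' below) is always on the causal side, and subject or environmental factors ('other factors') are the only rivals:

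- *Likely*: a well-known effect of either, and not explained by other factors.
- *Probably*: a known or suspected, but not well-known, effect of either, and not readily explained by other factors.
- *Possibly*: a possible, suspected or known effect of either that other factors could also explain. This is also the default for any event that fits no other grade, including unexplained events.
- *Unlikely*: not a suspected effect of either, and more plausibly, but not clearly, explained by other factors.
- *Unrelated*: not a suspected effect of either, and clearly explained by other factors.

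Add that if two grades still fit, the more related one is assigned. The default closes the gap that a bare change from 'or' to 'and' would open, and the tie-break removes remaining overlap. State that *likely*, *probably* and *possibly* count as related in 7.2 and 7.4.2.

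The cost is one paragraph and the matching case report form labels. Slightly more events may be graded related. Treatment, visits and sample size do not change.

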7.4 Reporting of Adverse Events, Adverse Device Effects and Unanticipated Problems

Investigators and the protocol sponsor (which may or may not be a Penn Investigator) must conform to the adverse event reporting timelines, formats and requirements of the various entities to which they are responsible,

If the report is supplied as a narrative, the minimum necessary information to be provided at the time of the initial report includes:

- Study identifier
- Study Center
- Subject number
- A description of the event
- Date of onset
- Current status
- Whether study intervention was discontinued
- The reason why the event is classified as serious
- Investigator assessment of the association between the event and study intervention

Additionally, all other events (unanticipated problems, adverse reactions, unanticipated adverse device effects) and subject complaints will be recorded and reported with respect to institutional and federal policies.

7.4.1 Follow-up report

If an SAE has not resolved at the time of the initial report and new information arises that changes the investigator's assessment of the event, a follow-up report including all relevant new or reassessed information (e.g., concomitant medication, medical history) should be submitted to the IRB. The investigator is responsible for ensuring that all SAE are followed until either resolved or stable.

CONFIDENTIAL

7.4.2 Investigator reporting: notifying the study sponsor

Investigators from all participating sites should report all unexpected and related adverse events, regardless of whether they are serious or not, and all unanticipated problems to the sponsor.

Any study-related unanticipated problem posing risk to subjects or others, and any type of serious adverse event, will be reported to the study sponsor by telephone within 24 hours of the event. To report such events, a Serious Adverse Event (SAE) form will be completed by the investigator and emailed to the study sponsor within 24 hours. The investigator will keep a copy of this SAE form on file at the study site. Report serious adverse events by sending via email to: [Evolus., Company Call Center: [name] ([name]), Company Email: [contact]]

Within the following 48 hours, the investigator will provide further information on the serious adverse event or the unanticipated problem in the form of a written narrative. This should include a copy of the completed Serious Adverse Event form, and any other diagnostic information that will assist the understanding of the event. Significant new information on ongoing serious adverse events should be provided promptly to the study sponsor.

7.4.3 Investigator reporting: notifying the Penn IRB

For single and multi-site studies each site PI will need to follow their local IRB reporting requirements in addition to the protocol outlined reporting.

7.4.4 Sponsor reporting: Notifying Participating Investigators

For clinical trials, in addition to reporting certain unanticipated problems and adverse events noted above to the FDA, it is the responsibility of the study sponsor to report those same adverse events or findings to participating investigators.

7.5 Medical Monitoring

It is the responsibility of the site Principal Investigator to oversee the safety of the study at his/her site. This safety monitoring will include careful assessment and appropriate reporting of adverse events as noted above. The lead PI will monitor all AEs reported.

7.6 Confidentiality

Information about study subjects will be kept confidential and managed according to the requirements of the Health Insurance Portability and Accountability Act of 1996 (HIPAA). Those regulations require a signed subject authorization informing the subject of the following:

- What protected health information (PHI) will be collected from subjects in this study
- Who will have access to that information and why
- Who will use or disclose that information
- The rights of a research subject to revoke their authorization for use of their PHI.

In the event that a subject revokes authorization to collect or use PHI, the investigator, by regulation, retains the ability to use all information collected prior to the revocation of subject authorization. For subjects that have revoked authorization to collect or use PHI, attempts should be made to obtain permission to collect at least vital status (i.e. that the subject is alive) at the end of their scheduled study period.

CONFIDENTIAL

7.7 Data Collection and Management

REDCap will be used to store and maintain the primary study records. The data entered into REDCap will be obtained from the study-relevant patient EMRs. Study personnel will be granted access to this project created in REDCap with each user obtaining individual access authenticated by a login system. Minimal patient identifiers will be collected and stored in the REDCap database. Patient name and date of birth will be collected in REDCap.

Source data will mainly be from the patient's EMR. When the study requires data not normally collected in the patient's EMR, the case report forms will also be the source document. Data from source documents (Appendix 15.4, case report forms (case report forms definition- Appendix 15.5), will be entered into an electronic data capturing system. All source documents should be secure in private spaces with restricted access. After Visit 1 the FACE-Q will be sent electronically to the subject for each follow-up visit via a REDCap survey.

During procurement of data charts will be reviewed in private spaces to ensure the confidentiality of acquired data. Data will be stored for up to 7 years after completion of the last follow-up visit of the last patient randomized. Data may be collected for up to two years following the treatment.

7.8 Records Retention

The Principal Investigator at each site is responsible for storing regulatory documents, subject files and financial records for the period specified by law. The time period for maintaining research records is defined first by HIPAA regulations that require any HIPAA-regulated information, authorizations, waivers, etc. must be maintained for at least 6 years subsequent to the Institutional Review Board (IRB) acknowledgement of the termination of the research project and secondly by DHHS regulations (45 CFR 46.115) and FDA regulations (21 CFR 56.115) state that IRB records relating to research shall be retained for at least 3 years after completion of the research.

8 Study Monitoring, Auditing, and Inspecting

8.1 Study Monitoring Plan

This study will be closely monitored by the PI and the project manager. The PI will be participating and the data will be collected by the PI and one other study team member from the patient's EMR. The study team member will enter the data into the REDCap and the project manager will monitor the entry to verify the compliance with respect to the protocol, data collection, and source documents.

8.2 Auditing and Inspecting

The investigator will permit study-related monitoring, audits, and inspections by the EC/IRB, the sponsor, government regulatory bodies, and University compliance and quality assurance groups of all study related documents (e.g. source documents, regulatory documents, data collection instruments, study data etc.). The investigator will ensure the capability for inspections of applicable study-related facilities (e.g. pharmacy, diagnostic laboratory, etc.).

Participation as an investigator in this study implies acceptance of potential inspection by government regulatory authorities and applicable University compliance and quality assurance offices.

CONFIDENTIAL

9 Ethical Considerations

This study is to be conducted in accordance with applicable US government regulations and international standards of Good Clinical Practice, and applicable institutional research policies and procedures.

This protocol and any amendments will be submitted to a properly constituted independent Ethics Committee (EC) or Institutional Review Board (IRB), in agreement with local legal prescriptions, for formal approval of the study conduct. The decision of the EC/IRB concerning the conduct of the study will be made in writing to the investigator and a copy of this decision will be provided to the sponsor before commencement of this study.

All subjects for this study will be provided a consent form describing this study and providing sufficient information for subjects to make an informed decision about their participation in this study. This consent form will be submitted with the protocol for review and approval by the EC/IRB for the study. The formal consent of a subject, using the EC/IRB-approved consent form, must be obtained before that subject undergoes any study procedure. The consent form must be signed by the subject or legally acceptable surrogate, and the investigator-designated research professional obtaining the consent.

9.1 Risks

All treatments used in this protocol will be used according to the FDA approved intended use. No unexpected risks should occur. Risks/side effects of injections include skin infection, redness, swelling, pain, tenderness, firmness, lumps/bumps, bruising, discoloration, itching, and dryness. Specific risks from dermal filler injections include unintentional injection into a blood vessel. This is a serious complication and may be permanent, although rare. Sequela of this complication can include vision abnormalities, blindness, stroke, skin necrosis or scarring.

There is minimal risk from the 3D imaging involved in this study to make volumetric measurements. The images will be identifying as they are of the face. All identifying images will be stored on a database or computer behind the firewall and a password.

Subjects should not be injected if they are allergic to lidocaine or Gram-positive bacterial proteins used in Juvéderm products or if they have had a previous allergic reaction to hyaluronic acid fillers.

The product has not been studied in pregnancy or breastfeeding patients, so these patients will be excluded.

